
Describe the project objectives and all the procedures that will be conducted for the proposed project (e.g. participant identification, data collection, data analysis, etc.): [HELP?](#)

Visit schedule: Baseline (pre-treatment), 1 month (questionnaires only), 3 months post PAP initiation. Participants will receive the 3 intervention sessions between baseline and 1 month.

Study design

Overall design: The overarching hypothesis of this study is that patients and partners who complete the couples based sleep health intervention (We-PAP) will have greater PAP adherence, improvements in sleep and quality of life compared to patients and partners with standard care plus information (IC). In this phase 2 trial, we will be adapting and testing the intervention modules then will conduct a 2-arm randomized controlled trial of the novel We-PAP intervention in comparison to IC.

Couples will be randomized in a 1:1 ratio using a randomization table created by the study statistician ([name]). Allocation will be concealed through using the online randomizer module in the RedCap data management system.

The study will be conducted over 20 months. The duration of participation for participants will be 3.5 months. Participants will complete a baseline assessment (pre-treatment), then 3 intervention sessions via telehealth. They will complete questionnaires at 1 month, then complete a final 3 months post treatment initiation assessment. This is a single site trial with multiple recruitment locations at the University of Utah Sleep Center and community clinics in the Salt Lake City area.

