4.4 Statistical Design and Power

General considerations

All statistical analyses will be estimated using Stata v15 or higher. Descriptive statistics for Aim 1 will be calculated using all available data, and tests of hypotheses for Aim 2 will be performed using intent-to-treat approaches that include all participants randomized to a treatment condition regardless of whether they complete the intervention or not. Following enrollment of the full sample, treatment group differences in baseline demographic and sleep related functioning variables will be tested. Any variables that emerge as being significantly different between the two treatment groups will be included as covariates in all tests of Aim 2. If more than 3 variables emerge as being significantly different between the treatment arms, the full set of demographic and sleep related functioning variables will be used to estimate a propensity score indicating likelihood of membership in We-PAP relative to information control (IC); this propensity score will be included as a covariate in all tests of Aim 2.

Given the pilot nature of the proposed study, significance tests of study hypotheses will be performed using one-sided tests with $\alpha = 0.10$. Research concerning statistical criteria for pilot testing of clinical trials¹¹⁰ suggest that these relaxed statistical criteria, with an emphasis on a priori defined confidence intervals, are appropriate because the primary purposes of the proposed study are to evaluate whether there is reasonable evidence that We-PAP outperforms IC and, if so, to use this initial evidence to plan for a larger scale RCT of We-PAP. We will use these criteria with the primary adherence outcomes as a go/no go threshold for proceeding to a larger scale RCT. Provided that We-PAP outperforms IC as hypothesized, we will continue to use these criteria in estimating the 90% CI of the between group difference to determine the necessary sample size for a subsequent RCT. Because of the well-known phenomenon of pilot trials generating larger effect sizes than follow-on RCTs, we will use the lower limit of the 90% CI to anticipate this reduction in effect size and conservatively plan for a larger study.

Sample Size Determination

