Power estimates were generated using descriptive statistics for behavioral and cognitive behavioral CPAP interventions vs. IC reported in Wozniak et al.¹¹¹. For % nights with CPAP usage ≥ 4 hours, We-PAP adherence was assumed to be 47% and IC adherence was assumed to be 28%. For total hours of CPAP usage per night, We-PAP usage was assumed to be 5.44 hours/night and IC usage was assumed to be 4 hours/night with a SD of 2.12 hours/night within each group. Power estimates based on these assumptions indicate that a sample size of 20 couples per group will provide power of .8 or higher to detect between group differences of $d = .68$ for average hours of CPAP usage and O.R. = 4.36. These required effect sizes are consistent with the medium to large differences in adherence outcomes between behavioral treatments for CPAP and IC reported in Wozniak et al., 2014¹¹¹. Power estimates for patient and partners' sleep [actigraphy and diary-assessed] were generated using descriptive statistics for behavioral and cognitive behavioral CPAP interventions vs. IC as reported in Wozniak et al.,¹¹¹ as well as in Buysse et al.,⁵⁸ and Sweetman et al¹¹². Assumptions for secondary outcomes were: sleep efficiency, We-PAP: $M = 82.2$, $SD = 1.16$, IC: $M = 79.99$, $SD = 1.15$; daytime sleepiness, We-PAP: $M = 4.9$, $SD = 0.3$, IC: $M = 5.2$, $SD = 0.45$. Power estimates for secondary outcomes were not available for differential treatment effects of CBT vs. IC for health-related quality of life, cognitive functioning, or relationship quality. Therefore, consistent with other psychosocial outcomes (e.g., depression, anxiety, etc.), differential treatment effects were assumed to be moderate to large, $d = .7$. The availability of these outcomes for both patients and partners permitted estimation of power for MLMs with adjustment made for assumed associations ($r = .3$) between relationship partners within a couple. Power estimates based on these assumptions indicate that a sample size of 20 couples per group will provide power of .8 or higher to detect between group differences of $d = .54$ for all outcomes, which is smaller than or equal to effect sizes for all outcomes described above.

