A final consideration in the determination of the sample size for the proposed study was the necessary sample size for stable and precise estimates of treatment effects using multilevel modeling. Maas and Hox's (2005)¹¹³ canonical work on necessary sample sizes for group level effects in MLM determines that group sizes of 20 members and larger is sufficient for generating unbiased estimates. Given that primary questions center on treatment effects in the proposed study, 20 couples per treatment ensures an adequate sample size for generating unbiased estimates of treatment effects thus permitting use of MLM to test study hypotheses.

Analysis Plan

Aim 2

Both primary outcomes will be analyzed using a two-level MLMs as described by the following series of equations:

$$\text{Level-1: } Y(\text{Adherence})_{ij} = \beta_{0j} + e_{ij}$$

$$\text{Level-2: } \beta_{0j} = \pi_{0j} + \pi_{0[1 \text{ to } n]} * [\text{covariates determined by tests of between group differences at baseline in demographic and sleep variables}] + \pi_{0[n+1]} * [\text{Treatment}] + \mu_{0j}$$

where i represents daily measures total hours of CPAP use/whether total hours of CPAP ≥ 4 hours (0 = no, 1 = yes) over the 3 month follow-up and j represents individuals. Treatment is a dummy coded variable with 0 = IC and 1 = We-PAP. The level two intercept in this model, π_{0j} , represents the maximum likelihood estimate of average adherence and $\pi_{0[n+1]}$ provides a test of the primary study hypotheses. Separate models will be run for total hours of sleep and ≥ 4 hours of CPAP use as outcomes estimated using models with Gaussian and binomial distributions respectively.

Secondary outcomes will be analyzed using a three-level MLMs as described by the following series of equations:

$$\text{Level-1: } Y(\text{Outcome})_{ijk} = \beta_{0jk} + \beta_{1jk} * (\text{Pre vs. 3 month follow-up}) + e_{ijk}$$

$$\text{Level-2: } \beta_{0jk} = \pi_{00k} + \pi_{0[1 \text{ to } n]k} * [\text{covariates determined by tests of between group differences at baseline in demographic and sleep variables}] + \pi_{0[n+1]k} * (\text{Patient vs. partner}) + \mu_{0jk}$$

$$\beta_{1jk} = \pi_{1jk} + \pi_{1[n+1]k} * (\text{Patient vs. partner})$$

$$\text{Level-3: } \pi_{0jk} = \gamma_{000} + \gamma_{001} * [\text{Treatment}] + r_{00k}$$

$$\pi_{1jk} = \gamma_{100} + \gamma_{101} * [\text{Treatment}]$$

$$\pi_{1[n+1]k} = \gamma_{1[n+1]0} + \gamma_{1[n+1]1} * [\text{Treatment}]$$

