where i represents repeated measurement of the outcome variable, j represents individuals, and k represents couples. Treatment is a dummy coded variable with 0 = IC and 1 = We-PAP; Pre vs. 3 month follow-up is a dummy coded variable with 0 = pre-treatment and 1 = 3 month follow-up; and, patient vs. partner is a dummy coded variable with 0 = patient and 1 = partner. The level three intercept in this model, π_{0jk} , represents the maximum likelihood estimate of average outcome, π_{1jk} provides a test of differential treatment effects, and $\pi_{1[n+1]k}$ provides a test of whether these effects differ for patients and partners. Separate models will be run for each outcome.

Missing Data. Mechanisms of missingness will be evaluated in outcomes and potential mediators with missing data. If missingness patterns are consistent with MAR assumptions, recently developed fully conditional specification with chained equations methods for multiple imputation of missing data in MLMs will be used to handle missing data^{114,115}. All variables in hypothesis tests plus additional auxiliary variables will be included; potential auxiliary variables will be carefully screened using methods recommended for small sample sizes¹⁰³. If missingness patterns are consistent with MNAR assumptions, we will consider the use of pattern mixture models¹⁰⁴ and conditionally dependent dropout¹¹⁶ models to minimize any potential bias in estimation of treatment effects.

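### The secondary-outcome model estimates a baseline arm difference that randomization makes zero, which costs precision, and the stated power of .8 at d = .54 is not the power of the coefficient it tests

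*SAP*

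**What the plan says.** SAP section 4.4, Analysis Plan, Aim 2: "Secondary outcomes will be analyzed using a three-level MLMs as described by the following series of equations". The time variable is defined as follows: "Pre vs. 3 month follow-up is a dummy coded variable with 0 = pre-treatment and 1 = 3 month follow-up". The Level-3 intercept carries γ₀₀₁ × Treatment and the Level-3 time slope carries γ₁₀₁ × Treatment. The text names the slope as the test of the treatment effect, with a separate term for whether the effect differs by role. Role is coded so that "patient vs. partner is a dummy coded variable with 0 = patient and 1 = partner". Covariates appear only in the intercept equation, and the rule for choosing them, under General considerations, is: "Any variables that emerge as being significantly different between the two treatment groups will be included as covariates in all tests of Aim 2".

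Sample Size Determination states power of .8 or higher at d = .54 with 20 couples per group and a within-couple partner correlation of .3, "for all outcomes, which is smaller than or equal to effect sizes for all outcomes described above". For quality of life, cognition and relationship quality, "differential treatment effects were assumed to be moderate to large", at d = .7. No pre-post correlation is given, and the SD that scales d is not named.

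Protocol, Study design: "Couples will be randomized in a 1:1 ratio using a randomization table created by the study statistician".

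**The concern.** There are two linked problems.

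**Precision.** A model with both γ₀₀₁ and γ₁₀₁ is a difference-in-change analysis. Under randomization the expected baseline difference is zero, so estimating it adds noise to the treatment effect. A model with a common baseline mean, or an ANCOVA on the 3-month value, uses the same data with a smaller standard error. The covariate rule does not repair this. It is triggered only by a significant baseline imbalance, and its terms enter the intercept rather than the change.

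**Power.** A Treatment × time calculation needs a pre-post correlation, or a statement that d is in SDs of change. The SAP gives neither. It also does not say whether d = .54 refers to patients, which is what γ₁₀₁ measures with patient = 0, or to the average over both roles.

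At stake are the standard errors for patient and partner sleep, quality of life, cognition and relationship quality, and whether a reader can rely on .8 power for the test that will be run.

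**Working it through.** **Inputs from the documents:** 20 couples per arm, 1:1 allocation, partner r = .3, d = .54 and d = .7, one-sided α = .10.

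**Assumptions:** outcome variance 1; the random-intercept structure as written (couple variance .3, person variance ρ − .3, residual 1 − ρ, so ρ is at least .3); complete data; d in outcome SDs unless stated; ρ = .3, .5, .7; noncentral t with 38 df.

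**Step 1. Reproduce the stated power.** At one time point a couple mean has variance (1 + .3)/2 = .65. The arm difference has variance 2 × .65/20 = .065. Then .54/√.065 = 2.118, and power is 0.799 (normal) or 0.792 (t). The stated figure is recovered without any ρ.

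**Step 2. Role-averaged Treatment × time as written.** The couple-mean change has variance 1 − ρ, so V = 2(1 − ρ)/20 = (1 − ρ)/10 = .0700/.0500/.0300.

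**Step 3. Role-averaged effect with a shared baseline.** The couple means at the two times correlate R = (.3 + ρ)/1.3 = .462/.615/.769. V = .065(1 − R²) = .0512/.0404/.0265.

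**Step 4. Patient coefficient γ₁₀₁.** This equals the role-averaged effect minus half the partner-minus-patient difference in effect. The model has no baseline Treatment × role term, so that difference is already baseline-adjusted. The within-couple difference has variance 2(1 − .3) = 1.4 and pre-post correlation q = (ρ − .3)/.7 = 0/.286/.571. Its contribution is ¼ × (2 × 1.4/20)(1 − q²) = .035(1 − q²) = .0350/.0321/.0236, added to the variances in steps 2 and 3.

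| ρ | Target | V as written | V shared baseline | Variance cut | Power at d = .54, written → shared | Couples/arm the written model needs to match 20 |
|---|---|---|---|---|---|---|
| .3 | role-averaged | .0700 | .0512 | 27% | 0.77 → 0.86 | 27 |
| .5 | role-averaged | .0500 | .0404 | 19% | 0.87 → 0.92 | 25 |
| .7 | role-averaged | .0300 | .0265 | 12% | 0.96 → 0.98 | 23 |
| .3 | patient, γ₁₀₁ | .1050 | .0862 | 18% | 0.64 → 0.70 | 24 |
| .5 | patient, γ₁₀₁ | .0821 | .0725 | 12% | 0.72 → 0.76 | 23 |
| .7 | patient, γ₁₀₁ | .0536 | .0501 | 6% | 0.85 → 0.87 | 21 |

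The last column is 20 × (V as written / V shared).

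**Step 5. Where the written model reaches .8 at d = .54.** Role-averaged: ρ of about 0.36–0.37 (0.79 at ρ = .35). Patient: ρ of about 0.63–0.64.

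**Step 6. If d is in SDs of change.** Multiply d by √(2(1 − ρ)). For the role average ρ cancels: .54 × √20 = 2.415, power 0.87. For γ₁₀₁ the ratio .54√(2(1 − ρ))/√V is 1.97/1.88/1.81, power about 0.75/0.72/0.69.

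**Step 7. At the planning effect d = .7, ρ = .3.** Power as written is 0.91 (role-averaged) or 0.80 (patient).

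**Step 8. Covariates in the intercept only.** With complete data a couple-level covariate cancels from the change, so γ₁₀₁ is unmoved. A person-level covariate leaves the role-averaged effect unmoved but can shift γ₁₀₁, because there is no baseline Treatment × role term. In 300 simulated data sets (assumed covariate effect .5 SD, ρ = .5) the shift averaged 0.06 SD, with a maximum of 0.30.

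**The case against.** - **The power figure could be change-based.** The role-averaged Treatment × time contrast also gives 0.799 if d is in SDs of change and partners' changes correlate .3, or in outcome SDs with ρ = .5 and that same correlation of changes. The SAP says the power was computed for multilevel models, so this reading is possible. It stands for the role average only. The coefficient the SAP names as the test is patient-coded, and under the written variance structure it stays below .8 on the change-SD scale (step 6).
- **Baseline might be measured after allocation.** The documents call it pre-treatment and do not say pre-randomization. If knowledge of the arm shifted baseline values by δ, a shared-baseline model could be biased. This does not favour the written model: a pure baseline shift biases difference-in-change by the full −δ, against −Rδ with R below 1. The order of baseline assessment and randomization should still be stated.
- **The gain is modest.** For γ₁₀₁ the standard error falls only 9/6/3% at ρ = .3/.5/.7, and d = .54 is a detectable effect, not the planning effect. The planning effects are larger: d = .7 for the psychosocial outcomes, 0.3/√((0.3² + 0.45²)/2) = .78 for sleepiness, and about 2.21/1.155 = 1.9 for sleep efficiency. This stands and limits the consequence. It does not justify giving up precision that costs nothing to keep.

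**Conclusion.** The concern holds on both counts.

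1. Estimating a baseline arm difference inflates the variance of the secondary treatment effects for any ρ below 1. Removing it cuts variance by 12–27% (role-averaged) or 6–18% (patient coefficient) over ρ = .3 to .7.
2. The stated .8 at d = .54 does not describe γ₁₀₁. This does not mean power is always below .8: it may fall on either side, depending on ρ, the scale of d and the target, none of which the SAP ties to the figure.

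This is a matter of efficiency and reporting, not validity, because both analyses are unbiased under randomization. It concerns secondary outcomes only, and the adherence go/no-go is untouched. The sizes rest on the assumed ρ, the written random-intercept structure, partner r = .3 and no dropout. If partners' changes correlated .15 or .3, which the written model does not allow for, the role-averaged threshold for .8 at d = .54 in outcome SDs would rise to ρ = 0.45 or 0.51. The change should be made, but the trial does not depend on it.

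**What to change.** - Remove γ₀₀₁ × Treatment from the Level-3 intercept so that the arms share a baseline mean. Alternatively, model the 3-month value on its baseline, Treatment, role and Treatment × role, with a couple random intercept.
- Do this whether or not the arms differ significantly at baseline, and state that baseline is measured before allocation is known.
- Put any prespecified covariates in the equation for the 3-month outcome.
- Restate the power with the assumed ρ, the SD that scales d, and whether the target is the patient effect or the role average.

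The cost is one deleted model term (or an ANCOVA refit) and one rewritten power paragraph. Baseline values are already collected, so no participants or visits are added.

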Study title: We-PAP: A Couples-based Intervention for Sleep Apnea

NCT 04759157

Document date: September 9, 2020

1. Study Purposes and Objectives:

The objectives should be stated in such a way that the reader can determine the appropriateness of the study design. If appropriate, state the specific hypotheses being tested and/or study aims. Use lay language.

The purpose of this study is to develop, refine and evaluate the feasibility of a novel couples-based intervention to improve adherence for patients with OSA.

Aims and Hypotheses Aim 1: To develop and refine the treatment and training materials for the We-PAP intervention, and pilot test treatment modules. The development phase includes adaptation of the existing transdiagnostic sleep and circadian program materials for our target population (patients with OSA and partners), development of study manuals, session and training materials, and patient handouts. The refinement phase will consist of focus groups with key stakeholders and a field test in 4 couples in order to make adjustments prior to the randomized pilot trial.

Aim 2: To evaluate the feasibility, treatment satisfaction and preliminary efficacy of We-PAP versus IC in a sample of 40 OSA patients and their partners (i.e., 20 couples per treatment arm). Feasibility measures include completion and ratings of treatment satisfaction. Outcomes including PAP adherence (primary, patient only), and patient and partners' sleep (actigraphy and diary-assessed), relationship quality, quality of life (QOL), and cognitive function measured at baseline (prior to initiation of PAP treatment) and at 3 months follow-up. Hypothesis: We predict that patients in the WePAP intervention will demonstrate higher PAP adherence compared to the IC at 3 months. We also hypothesize that patients and partners will demonstrate better self-reported and objective sleep quality and greater improvement in other patient reported outcomes such as quality of life.

1. Background and Introduction:

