Control group description: We will compare our novel We-PAP intervention to a standard information control group (IC), which includes standardized educational materials published by the American Academy of Sleep Medicine. The materials are standardized educational pamphlets that are available at the sleep wake center and provided to patients. In this study we will be mailing out the materials (right now they are usually just available in the waiting room and handed out by some but possibly not all of the doctors)

Session administration: Participants in the We-PAP will receive 3, sessions conducted weekly via Zoom (depending on the couple's comfort with each platform). Given the challenges to recruiting couples, use of telehealth will increase the flexibility for scheduling with couples. For example, they will not need to find child care to attend the session together. The use of telehealth will allow patients and partners to complete the intervention at home or even if the couple is in separate locations. Session content will be presented via a slide presentation and will include videos and testimonials. Patients will also be provided with handouts from the sessions. Patients in the IC group will be mailed a packet of informational materials.

Study assessment and procedure

Screening assessments: Potential patients and partners will complete screening measures over the phone or via a web link to verify inclusion/exclusion criteria including demographics, a medical history and medication use questionnaire and various measures for inclusion/exclusion criteria. Couples where one or both report moderate to severe symptoms of restless legs syndrome on the International Restless Legs Working Group Questionnaire will be excluded. The PROMIS sleep disturbance questionnaire will be used to select participants with poor sleep quality (must be elevated in patient and/or partner for inclusion). Baseline (pretreatment) will be scheduled prior to initiation of PAP at home. Research staff will schedule to conduct this assessment at home or in the behavioral sleep medicine laboratory. The session will include consent, questionnaires, cognitive testing and training on actigraphy.

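### The secondary three-level model's named treatment test targets patients only; no test of the partners' effect is stated, and d = .54 matches the couple average instead

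*SAP*

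**What the plan says.** SAP 4.4, Analysis Plan, Aim 2: "Secondary outcomes will be analyzed using a three-level MLMs as described by the following series of equations". The pre-to-3-month slope is `π_1jk` plus `π_1[n+1]k` times role. Each of these has its own Treatment term at level 3: `γ_101` in the first and `γ_1[n+1]1` in the second. The text after the equations gives the coding, "patient vs. partner is a dummy coded variable with 0 = patient and 1 = partner". It says that `π_1jk` "provides a test of differential treatment effects" and that `π_1[n+1]k` "provides a test of whether these effects differ for patients and partners".

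SAP 4.4, Sample Size Determination, says of the secondary outcomes: "The availability of these outcomes for both patients and partners permitted estimation of power for MLMs". It assumes a within-couple correlation of .3 and reports power of at least .8 at d = .54 with 20 couples per arm. It does not name the effect to which .54 belongs.

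The protocol's hypotheses cover both roles. Section 1 (Aim 2): "We also hypothesize that patients and partners will demonstrate better self-reported and objective sleep quality". Study design, Overall design: "patients and partners who complete the couples based sleep health intervention (We-PAP) will have greater PAP adherence, improvements in sleep and quality of life". Under Screening assessments, raised sleep disturbance "must be elevated in patient and/or partner for inclusion", so a couple can qualify on the partner's poor sleep alone.

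**The concern.** With role coded 0 for patients, the role part of the slope vanishes for them, and `γ_101` is the treatment effect on change in patients. The SAP calls the term containing it the test of differential treatment effects and names no role, so a report that followed the plan could present a patients' effect as the treatment effect.

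Two things follow. First, the partners' half of the hypothesis has no stated test. If only partners benefit, `γ_101` is zero and the named test rejects only at its type I error rate. The role-difference test would respond, but a difference from patients is not an estimate of partners' benefit. Equal effects cannot be taken for granted, since only patients start PAP. Second, the power statement draws on both members of the couple, while the named test targets one.

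**Working it through.** **Inputs from the documents.** 20 couples per arm, 1:1; one-sided α = 0.10; power .80; r = .3 between partners; assumed d = .7 for quality of life, cognition and relationship quality. Outcome SD is set to 1. z(.90) + z(.80) = 1.2816 + 0.8416 = 2.1232.

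**1. What the coefficients mean.** Treatment effect on the slope = `γ_101` + `γ_1[n+1]1` × role.
- Patients (role 0): `γ_101`
- Partners (role 1): `γ_101` + `γ_1[n+1]1`
- Couple average: `γ_101` + 0.5 × `γ_1[n+1]1`

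The SAP names `π_1jk`, not `γ_101`. Reading the test as `γ_101` is an inference, but it is the only treatment coefficient in `π_1jk`.

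**2. The SAP's .54, post-treatment values only.**
- Couple average: SD = √((1 + .3)/2) = .806; SE = .806 × √(2/20) = .255; detectable d = 2.1232 × .255 = .541. Power at .54 = Φ(.54/.255 − 1.2816) = .799. With the t distribution: .547 and .792. This reproduces the stated figure.
- One role: SE = √(2/20) = .316; detectable d = .671. Power at .54 = Φ(.54/.316 − 1.2816) = .665. With t: .679 and .658. This does not reproduce it.

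**3. The model as printed (pre/post, random intercepts only).** The pre-post correlation ρ is not given in the SAP; .3 to .7 is assumed here. The printed random effects make the between-partner correlation the same within and across time points (.3). The equations have no baseline role-by-treatment term, so

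Var(`γ_101`) = (1 − ρ)/10 + (1/4)(1/10)[1.4 − 4(ρ − .3)²/1.4],

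where the first term is the variance of the couple-average effect and the bracket is the residual variance of the role difference.

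| ρ (assumed) | SE of `γ_101` | detectable d, `γ_101` | detectable d, couple average |
|---|---|---|---|
| .3 | .324 | .688 | .562 |
| .5 | .287 | .609 | .475 |
| .7 | .231 | .491 | .368 |

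`γ_101` reaches .54 when its variance is (.54/2.1232)² = .0647. At ρ = .627 the formula gives .0373 + .0350 − .0076 = .0647. So .54 holds for the named test only if ρ is about .63 or more.

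**4. Benefit in partners only, d = .7, post-only.**
- Named test `γ_101`: rejects at .10, its type I error.
- Role difference: SD = √(2 × .7) = 1.183; SE = .374; power = Φ(.7/.374 − 1.2816) = .72, one-sided in that direction.
- Partners' contrast: power = Φ(.7/.316 − 1.2816) = .82.

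**5. One-role power at the SAP's assumed effects, post-only.** At d = .7: .824 (t: .818). Sleepiness, d = .3/√((.3² + .45²)/2) = .784: .884. Sleep efficiency, d = 2.21/√((1.16² + 1.15²)/2) = 1.91: above .99.

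**The case against.** The strongest reply is that little changes. These are secondary outcomes in a pilot, the go/no-go rests on adherence through a separate patient-only model, and the assumed effects exceed what one role can detect. The power text, by using both members and r = .3, already points to a pooled effect, so only a label is missing. The partners' effect is a linear combination of the same fit and can be obtained at any time. A partner-only benefit is not ignored either, since the role-difference test has power .72 against .82 for a direct contrast.

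Most of this stands and limits the reach. It does not remove the point. The effect that the power text points to is not the effect that the model names as its test. Choosing among patient, partner and average after seeing the results is what prespecification is meant to prevent.

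A further objection is also fair: `γ_101` does not use patients' data alone. Because no baseline role-by-treatment term is printed, the estimate borrows partners' baselines. At ρ = .5 the baseline arm difference is weighted .5 + .5 × (.4/1.4) = .64 on patients and .36 on partners. The estimate equals the patients' effect in expectation under randomization, and that is the sense intended here.

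Finally, part of the SAP was not available to this review, so the absence of a partners' test is established only for the text seen.

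**Conclusion.** The point holds and should be fixed. As coded, the named treatment test targets the patients' effect, no test of the partners' effect is stated in the available text, and d = .54 reproduces for the couple average (.541) and not for one role (.67 to .68; power about .66 at .54). The coding result needs no assumption beyond reading the test as `γ_101`. The .54 comparison rests on the SAP's inputs and a post-only calculation; the pre/post figures rest on an assumed ρ.

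Three stronger readings are not supported:
- *The secondary analyses are underpowered.* At the assumed effects, one-role power is about .82 or higher post-only. In the printed model, detectable d for `γ_101` stays at .49 to .69, below .7, for ρ from .3 to .7. Values up to .77 need a lower between-partner correlation across time than within time, which the printed random effects exclude.
- *The printed model inflates type I error, so a random slope is needed.* Within the printed covariance structure the level is exactly .10. Rates of about .11 to .13 arise only under other covariances, using correlations that the SAP does not give.
- *The couple average ought to be the main test.* That is a choice of estimand. It is more precise when effects are similar. When the partners' effect is below about 61% of the patients' (2 × .806 − 1 = .61, post-only), `γ_101` has more power.

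**What to change.** In SAP 4.4, Analysis Plan, after the three-level equations:
- State that `γ_101` is the treatment effect on change in patients.
- Prespecify the partners' contrast, `γ_101` + `γ_1[n+1]1`, from the same fit.
- Report each with its 90% CI, and keep the role-difference test.

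In SAP 4.4, Sample Size Determination:
- Label d = .54 as a post-only couple-average figure.
- Add the single-role figure: about .67 to .68 post-only, or a value for the pre/post model with its pre-post correlation stated.

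The cost is a sentence or two in each place and one linear-combination command in Stata, with no new data and no burden on participants. The downside is one more test per secondary outcome at one-sided 0.10, which the report should acknowledge. Making the couple average the main test, or adding a couple-level random time slope, is optional and not part of this fix; the slope may be unstable with 40 couples.
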